## **COVARIATES AND SECONDARY OUTCOME MEASURES**

### **5.8.11 Modified NASA Task Load Index (NASA-TLX)**

The NASA Task Load Index (NASA-TLX) is a series of single-item visual analog scales that ask participants to evaluate their performance across six domains. Responses in each domain translate to a point score of 1 (lowest) to 21 (highest). For the purposes of our study, we will ask participants to self-evaluate their performance across four domains: mental demand, performance, effort, and frustration. It will be administered following each cognitive task (DMS, HVLT-R, RVP, OTS, Digit Span, COWA, ANT). The NASA-TLX will take no greater than 7 minutes to complete. All participants who are enrolled in the trial will be evaluated pre- and post-chemotherapy.

### **5.8.12 Patient Reported Outcomes Measurement Information System – Depression (PROMIS-D)**

The National Institute of Health's Patient-Reported Outcomes Measurement Information System (PROMIS) contains a depression bank. We will use the PROMIS Depression 8a short form. Higher scores represent greater degrees of depression. The PROMIS-D will take less than 2 minutes to complete. All participants who are enrolled in the trial will be evaluated pre- and post-chemotherapy.

### **5.8.13 Patient Reported Outcomes Measurement Information System – Anxiety (PROMIS-A)**

The National Institute of Health's Patient-Reported Outcomes Measurement Information System (PROMIS) contains an anxiety bank. We will use the PROMIS Emotional Distress-Anxiety – Short Form 6a. Higher scores represent greater degrees of anxiety. The PROMIS Anxiety will take less than 2 minutes to complete. All participants who are enrolled in the trial will be evaluated pre- and post-chemotherapy.

### **5.8.14 Patient Reported Outcomes Measurement Information System – Sleep Disturbance**

The National Institute of Health's Patient-Reported Outcomes Measurement Information System (PROMIS) contains sleep bank. We will use the PROMIS Sleep Disturbance Short Form. Higher scores represent greater sleep difficulties. The PROMIS Sleep Disturbance Short Form will take less than 2 minutes to complete. All participants who are enrolled in the trial will be evaluated pre- and post-chemotherapy.

#### **5.8.15 Functional Assessment of Chronic Illness Therapy-Fatigue (FACIT-F)**

The FACIT-F scale is a 13-item scale that uses a 5-point Likert-type scale (0=not at all, 1=a little bit, 2=somewhat, 3=quite a bit, 4=very much). The suggested FACIT-F cut-point for significant fatigue is 36 on a 0 to 52 scale (lower scores indicating greater fatigue). The FACIT-F scale is written at the 4th grade level (Lexile framework) and takes 2-3 minutes for an average person to complete. FACIT-F will be measured pre- and post-chemotherapy.

#### **5.8.16 Patient-Reported Karnofsky Performance Status (Patient-KPS)**

The Patient-reported KPS provides a self-characterization of functional status, ranging from severely/require continuous nursing care to normal/no complaints/no symptoms of disease. Scores range from 30 to 100. Higher scores indicate better function. The Patient-KPS will take less than 2 minutes to complete. All participants who are enrolled in the trial will be evaluated pre- and post-chemotherapy.

#### **5.8.17 Functional Assessment of Cancer Therapy-General (FACT-G)**

The FACT-G is a 27-item patient-administered assessment of general quality-of-life measures in cancer patients. It has been validated in the literature and permits the measurement of a number of symptoms including nausea, pain, and insomnia. The FACT-G will take no greater than 5 minutes to complete. All participants who are enrolled in the trial will be evaluated pre- and post-chemotherapy.

#### **5.8.18 Hormonal Status**

We have developed a brief measure to assess multiple dimensions of hormonal status. Four items inquire about participants' menstrual cycles to ascertain pre-, peri-, or post-menopausal status per the Stages of Reproductive Aging Workshop + 10 (STRAW +10) criteria. These items will be used in conjunction with FSH levels to clarify participants' menopausal status. Five items assess hormone sensitivity by inquiring about experiences with hormone replacement therapy, oral contraceptives, and mood changes related to menstrual cycle, pregnancy, or postpartum period. The Hormonal Status Questionnaire will take fewer than 5 minutes to complete. All participants will complete the hormonal status assessment pre- and post-chemotherapy.

#### **5.8.19 Modified Brief Medication Questionnaire (BMQ)-Specific**

The BMQ-Specific contains two five-item scales assessing patients' personal beliefs about the necessity and concerns of taking prescribed medication for their illness. We will use a modified version of this instrument consisting of statements specific to memantine and cognition. The Modified BMQ-Specific uses a 5-point Likert-type scale (1=strongly disagree to 5=strongly agree) to indicate participants' agreement with each statement. Total scores for the necessity and concerns scales range from 5 to 25 and are calculated by summing the individual item scores within each scale. Higher scores represent greater belief in efficacy and greater concerns, respectively. The Modified BMQ-Specific will

take fewer than 5 minutes to complete. All participants who are enrolled in the trial will be evaluated post-chemotherapy and those who withdraw will be offered to complete the assessment at the time of study withdrawal.

## 6.0 DRUG INFORMATION

### 6.1 Memantine Description and Management

#### 6.1.1 Mechanism of Action

Memantine HCl is a low to moderate affinity uncompetitive (open-channel) NMDA receptor antagonist. It binds preferentially to central nervous system NMDA receptor-operated cation channels. Additionally, memantine has antagonistic effects at the 5HT3 receptor and blocks nicotinic acetylcholine receptors at 10-16% potency relative to its action on NMDA and 5HT3 receptors.

#### 6.1.2 Indications

Memantine HCl is indicated for the treatment of moderate to severe dementia of the Alzheimer type.

#### 6.1.3 How Supplied

The drug will be obtained from commercial supply through UNC Pharmacy and UNC Investigational Drug Service (IDS).

Full prescribing information for (Memantine HCl) is available at:

[https://www.accessdata.fda.gov/drugsatfda\\_docs/label/2013/021487s010s012s014\\_021627s008lbl.pdf](https://www.accessdata.fda.gov/drugsatfda_docs/label/2013/021487s010s012s014_021627s008lbl.pdf)

#### 6.1.4 Dosage and Administration:

Participants will receive a gradual dose titration of memantine at 5 mg increments per week to a goal dose of 10 mg PO bid. Titration schedule is as follows:

- Week 1: 5 mg dose once daily
- Week 2: 5 mg dose twice daily
- Week 3: 5 mg each morning/10 mg each evening
- Week 4 through end of Chemotherapy: 10 mg dose twice daily

#### 6.1.5 Storage and Stability:

Memantine HCl should be stored at room temperature (between 59° to 77° F).

#### 6.1.6 Handling and Disposal:

Local requirements for disposal of hazardous drugs will be followed.

Please see UNC policy on hazardous drugs:

<http://intranet.unchealthcare.org/intranet/hospitaldepartments/safetynet/policies/hazardousdrugs.pdf>

### 6.1.7 Adverse Events Associated with Commercial Drug

In a meta-analysis of six phase III placebo-controlled trials of 959 patients receiving memantine HCl for moderate to severe Alzheimer's disease, the most frequently identified side effects were dizziness (6.3%), headache (5.2%), constipation (4.6%), and somnolence (3.4%). The following have also been reported with the following frequencies: confusion (6%), hypertension (4%), coughing (4%), pain (3%), hallucination (3%), vomiting (3%), dyspnea (2%), and fatigue (2%). A comprehensive list of adverse effects can be found at the following web address:

[https://www.accessdata.fda.gov/drugsatfda\\_docs/label/2013/021487s010s012s014\\_021627s008lbl.pdf](https://www.accessdata.fda.gov/drugsatfda_docs/label/2013/021487s010s012s014_021627s008lbl.pdf)

## 7.0 EVALUATIONS AND ASSESSMENTS

### 7.1 Time and Events Table

|                                    | Baseline (Pre-Chemotherapy) a | During Chemotherapy | Post-Chemotherapy b | 6 Months Post-Chemotherapy d |
|------------------------------------|--|---------------------|--------------------------------|---|
| Informed Consent                   | •  |                     |                                |   |
| Demographic Data Form              | •  |                     |                                |   |
| Cancer History Form                | •  |                     |                                |   |
| BOMC                               | •  |                     |                                |   |
| DMS                                | •  |                     | •                              | •                                       |
| HVLT-R                             | •  |                     | •                              | •                                       |
| RVP                                | •  |                     | •                              | •                                       |
| OTS                                | •  |                     | •                              | •                                       |
| Digit Span                         | •  |                     | •                              | •                                       |
| COWA                               | •  |                     | •                              | •                                       |
| ANT                                | •  |                     | •                              | •                                       |
| WTAR                               | •  |                     |                                |   |
| Modified PROMIS-Cognitive Function | •  |                     | •                              | •                                       |
| Modified NASA-TLX                  | •  |                     | •                              | •                                       |
| PROMIS-Depression                  | •  |                     | •                              | •                                       |
| PROMIS-Anxiety                     | •  |                     | •                              | •                                       |
| PROMIS-Sleep Disturbance           | •  |                     | •                              | •                                       |
| Hormonal Status                    | •  |                     | •                              | •                                       |
| FACIT-F                            | •  |                     | •                              | •                                       |
| Patient-KPS                        | •  |                     | •                              | •                                       |
| FACT-G                             | •  |                     | •                              | •                                       |
| Follicle Stimulating Hormone Level | •  |                     | • c                 |   |
| CNS-Active Medications             | •  | •                   |                                |   |

|  |  |   |   |  |
|--|--|---|---|--|
| Adverse Events Form                                    |  | • |   |  |
| Adherence  |  | • |   |  |
| Alternative CRCI treatments                            |  |   | • |  |
| Modified Brief Medication Questionnaire (BMQ)-Specific |  |   | • |  |

- a. Pre-chemotherapy assessments will occur any time between establishing care in the UNC Breast, Hillsborough Oncology, or UNC REX Cancer Center clinics and one week after the start of chemotherapy
- b. Post-chemotherapy assessments will occur 4 weeks after (range: 2-12 weeks after) last dose of chemotherapy
- c. FSH level will be obtained post-chemotherapy only in participants who reported still having menstrual cycles at the pre-chemotherapy assessment
- d. 6-month post-chemotherapy assessments will occur only in a subset of participants who volunteer for extended longitudinal follow-up

## 7.2 Pre-Study (Baseline) Assessments

Patients referred to the UNC Breast Center, Hillsborough Oncology, and UNC REX Oncology clinics will be considered for enrollment in this trial. Prior to chemotherapy initiation, the CRA or PI will review the trial with the participant, confirm eligibility, and obtain informed consent. The participant will complete a cognitive assessment battery, evaluating visual working memory (DMS), verbal learning and memory (HVLT-R), processing speed (RVP), executive function (OTS), attention and working memory (Digit Span), verbal fluency (COWA), semantic fluency (ANT), and intelligence quotient (WTAR). Self-reported cognitive effort associated with each task will be evaluated using the NASA-TLX. The participant will also complete self-report assessments of cognitive function (PROMIS-Modified Cognitive Function), depression (PROMIS-D), anxiety (PROMIS-A), hormonal status, sleep (PROMIS-Sleep Disturbance), fatigue (FACT-F), functional status (Patient-KPS), and HRQOL (FACT-G). See Appendices A – P. Follicle stimulating hormone (FSH) levels will be drawn to aid in determination of hormonal status. Following completion of all pre-study (baseline) assessments, participants will be compensated for their time with a gift card. Participants must complete all aspects of the study visit in order to receive the compensation. The CRA or investigators will also conduct a review of electronic medical records to obtain baseline information regarding medical/surgical history, the participant's cancer and cancer treatment, and demographic information. All study-related interactions will be conducted in private rooms at UNC Breast, Hillsborough Oncology, and UNC REX Cancer Center clinics; in private rooms at participants' homes; over the phone; and by video conferencing after confirming that subjects are in a private location. Study assessments and questionnaires will be offered by email and mail as is necessary and feasible.

### 7.3 Treatment

If the participant meets all inclusion/exclusion criteria and provides informed consent, she will receive memantine beginning within four weeks before and one week after chemotherapy initiation until the post-chemotherapy assessment, approximately four weeks after the last dose of chemotherapy (estimated total duration of memantine: 12-30 weeks). Tolerability of memantine and medication adherence will be serially assessed for the duration of treatment. Patients will be assessed at an interval no greater than every three weeks. For patients receiving anit-HER2 directed therapy in addition to chemotherapy, toxicity will only be assessed during the chemotherapy segment of the regimen. Tolerability will be assessed as described in section 5.3. Medication adherence will be tracked using number of patient-estimated missed doses since last assessment.

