## 1.0 BACKGROUND AND RATIONALE

### 1.1 Study Synopsis

This is a one-arm phase II interventional study in patients with breast cancer to investigate whether memantine can prevent cognitive decline during chemotherapy. We will recruit 56 participants with breast cancer referred to the UNC Breast Center, Hillsborough Oncology, or UNC REX Oncology clinics for initiation of adjuvant or neoadjuvant chemotherapy, perform a cognitive assessment at initiation (range: any time after establishing care to one week after first dose) and four weeks after completion of chemotherapy (range: two to twelve weeks after last dose), and treat with memantine 10 mg twice daily between the pre- and post-chemotherapy study assessments (estimated duration: 12-30 weeks). We will assess cognitive function objectively using a computerized cognitive assessment and a standard neuropsychological battery. To assess subjective cognitive function, we will use the Patient Reported Outcome Measurement Information System (PROMIS) Cognitive Function measure. Depression, anxiety, fatigue, menopausal status, and sleep are comorbidities known to affect cognitive function, and therefore will be assessed as covariates through self-report measures and, in the case of menopausal status, laboratory values. Depression, anxiety, health-related quality of life (HRQOL) and functional status will be evaluated as secondary outcomes. Cognitive and other secondary outcome measures will be repeated in a subset of participants who opt-in for longitudinal follow-up at 6 months (range: 4 to 8 months) post-chemotherapy. We will also assess the feasibility of our study by monitoring recruitment, retention, and adherence to memantine.

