#### 5.2 Treatment Dosage and Administration

Participants will receive memantine beginning within four weeks prior to and one week after chemotherapy initiation. All patients will be gradually titrated to 10 mg twice daily as follows: 5 mg daily in week 1, 5 mg twice daily in week 2, 5 mg each morning and 10 mg each evening in week 3, then 10 mg twice daily in week 4. Participants will continue 10 mg twice daily until 4 weeks (range: 2 to 12

weeks) after the last dose of chemotherapy. Depending on the chemotherapy regimen, total duration will range from approximately 12-30 weeks.

| REGIMEN DESCRIPTION |       |                                       |                                     |
|---------------------|-------|---------------------------------------|-------------------------------------|
| Agent               | Route | Dose                                  | Schedule                            |
| Memantine HCl       | Oral  | 5 mg daily                            | Week 1                              |
|                     |       | 5 mg twice daily                      | Week 2                              |
|                     |       | 5 mg each morning, 10 mg each evening | Week 3                              |
|                     |       | 10 mg twice daily                     | Week 4 to 4 weeks post-chemotherapy |

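### The synopsis places memantine between the two assessments, but the treatment and baseline windows in sections 5.2, 7.1 and 7.3 allow the baseline DMS to be taken after memantine has started

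*Combined protocol and SAP*

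**What the plan says.** Section 1.1 gives an order: "treat with memantine 10 mg twice daily between the pre- and post-chemotherapy study assessments". The same sentence gives the baseline range as "range: any time after establishing care to one week after first dose". I read the dose meant there as the first chemotherapy dose, because note a to the Time and Events Table (7.1) closes the baseline window at the same point relative to chemotherapy: "UNC REX Cancer Center clinics and one week after the start of chemotherapy".

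The start of memantine has its own window. Section 5.2: "Participants will receive memantine beginning within four weeks prior to and one week after chemotherapy initiation". Section 7.3 repeats it: "If the participant meets all inclusion/exclusion criteria and provides informed consent, she will receive memantine beginning within four weeks before and one week after", with treatment running to the second assessment. Titration takes three weeks, with full dose from the fourth: "5 mg each morning and 10 mg each evening in week 3, then 10 mg twice daily in week 4".

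Section 7.3 makes treatment conditional on eligibility and consent and does not name the baseline battery. Section 7.2 calls the baseline pre-study and places consent before chemotherapy, but gives the battery no time relative to memantine. Section 7.11 analyses everyone who enrols, takes at least one dose and completes the primary outcome measure. Section 9.3 plans no analysis by the timing of the baseline.

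**The concern.** Both windows are tied to chemotherapy and neither is tied to the other, so they can be met in the order opposite to the one in the synopsis.

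The primary endpoint (3.1) is each participant's change in DMS, tested in a single arm against a fixed historical increase of 5 points (9.2). No concurrent arm would share and cancel a shifted baseline. If memantine has a prompt effect on visual working memory, that effect sits in both scores of a participant with an on-drug baseline, and the measured change shrinks. If early side effects lower the on-drug baseline, the later change grows. Section 5.3 solicits dizziness, confusion and fatigue as common memantine effects, so the second route cannot be dismissed. The other cognitive tests and the self-report baselines, such as FACIT-F, are exposed in the same way.

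**Working it through.** **Step 1: the plan's own power.** Inputs from 9.2: difference 8 − 5 = 3 points, SD 7.97, n = 45, one-sided 0.05.
- Effect size: 3 / 7.97 = 0.376, as stated.
- Noncentrality: 0.376 × √45 = 2.52. The one-sided critical value on 44 degrees of freedom is 1.68.
- Noncentral t power: 80.0%. The stated figure reproduces, and this point does not dispute it.

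**Step 2: what the windows allow.** Day 0 is chemotherapy initiation. Memantine may start from day −28 to day +7, and baseline may be taken up to day +7. Days on drug at baseline = baseline day − start day. Days at full dose = days on drug − 21, if positive.

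| Memantine start | Baseline | Days on drug | Days at 10 mg twice daily |
|---|---|---|---|
| −28 | +7 | 35 | 14 |
| −28 | 0 | 28 | 7 |
| −21 | +7 | 28 | 7 |
| −21 | 0 | 21 | 0 |
| −14 | +7 | 21 | 0 |
| −7 | +7 | 14 | 0 |
| 0 | +7 | 7 | 0 |
| +7 | +7 | 0 | 0 |

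Full-dose exposure at baseline needs a start more than 21 days earlier. Most of the other combinations listed put the baseline within titration. If baseline is done before the first dose, exposure is nil whatever the start day.

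**Step 3: what an on-drug baseline could cost.** Let f be the share of participants with an on-drug baseline and g the share of the 3-point effect already present at that baseline. The documents give neither, so both are assumptions. The measurable difference is 3 × (1 − f × g). With n = 45 and the SD held at 7.97:

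| f | g = 0.25 | g = 0.50 | g = 1 |
|---|---|---|---|
| 0.10 | 2.925 points, 78% | 2.85 points, 76% | 2.70 points, 72% |
| 0.25 | 2.81 points, 75% | 2.625 points, 70% | 2.25 points, 59% |
| 0.50 | 2.625 points, 70% | 2.25 points, 59% | 1.50 points, 34% |

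If f = 0 or g = 0, power stays at 80%. Holding the SD fixed matters little: at f = 0.10 and g = 1 the mixing adds 0.10 × 0.90 × 3² = 0.81 to a variance of 7.97² = 63.5.

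The table covers only a benefit already present at baseline. A side-effect dip would act in the other direction, and the documents give no figure from which to size it.

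**The case against.** The strongest reply is that the order is already in the protocol. The synopsis is current text, and a first dose before the baseline DMS contradicts it. Section 7.2 calls the baseline pre-study and comes before the treatment section. Eligibility needs a BOMC score (4.2.4), and the BOMC belongs to the baseline battery, so dosing already depends on at least one baseline test. The schema in 5.1 is not visible in the text available to me and may draw the order.

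Most of this stands. A reader might infer that the protocol has no rule on order, or that an on-drug baseline is fully within protocol. The synopsis rules out both readings. What remains is that the order is not carried into the sections that staff work from. The labels do not settle it, since an assessment called pre-chemotherapy may itself fall a week after chemotherapy starts. The BOMC can be done on its own at screening, without the DMS.

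A second reply is that full dose at baseline is a corner case, and that the trial tests prevention of decline during chemotherapy, so little of the effect should be present at an early baseline. Both parts are fair: the first limits the exposure in most cases to titration doses, and the second favours a small g. Some exposure, though, needs no corner case. The Amendment 5 summary explains the wider start window as a way to get drug into participants before chemotherapy. Where that aim is met, any baseline done in the week after chemotherapy starts is an on-drug baseline.

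A reader might also turn the rates in 6.1.7 (confusion 6%, dizziness 6.3%) into an inflation of the result in memantine's favour. The documents do not support that. The dizziness rate comes from Alzheimer's disease trials and the confusion rate from the prescribing information, and neither is linked to a DMS change of any size.

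**Conclusion.** The concern holds as a conflict between the synopsis and the windows. As written, 5.2, 7.1 and 7.3 allow a baseline DMS on memantine, with at most 35 days on drug and 14 at 10 mg twice daily, and 7.11 would analyse that baseline like any other. In a single-arm comparison with a fixed historical change, this would bias the primary endpoint.

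Neither the direction nor the size can be stated from the documents, and they do not show how often, or whether, it happens. The power range of 78% to 72% at f = 10% is an illustration that rests on assumed f and g and on the plan's own n and SD. The maximum exposure follows from the stated windows and from reading the synopsis range as relative to the first chemotherapy dose. The point does not show that full-dose baselines are typical, that the result favours memantine, or that the sample size is wrong.

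**What to change.** Reconcile note a of 7.1, section 7.2 and section 7.3 with the synopsis by stating in each that all baseline cognitive and self-report assessments are completed before the first dose of memantine. Dose, titration and the chemotherapy-based windows are untouched.

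For participants already enrolled, compare the date of the baseline DMS with the date of the first memantine dose and report how many baselines came after it. The trial should hold both dates: adverse-event recording starts on day 1 of treatment (8.2), so that day has to be known. Before the data are analysed, add to 9.3 a sensitivity analysis of the primary endpoint that leaves out baselines taken after the first dose.

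The cost is one sentence in three places, one extra analysis, somewhat tighter scheduling of the baseline visit, and slightly fewer participants in the sensitivity analysis if any are excluded.
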